1.5 Rationale for the Doses Selected for the DBPCFC

The study DBPCFCs will be conducted in accordance with the recommended PRACTALL guidelines although the Screening DBPCFC will not exceed 300 mg (444 mg cumulative). This is to select subjects that are representative of approximately the more sensitive half of the peanut-allergic population (Section 1.3). The Exit DBPCFC will not go above a 1000 mg (2043 mg cumulative) dose to help ensure subject safety. Additionally, the DBPCFCs will progress through the dose levels in an unaltered sequence without repeating any dose to provide standardization of the amounts of peanut protein subjects are exposed to when being tested in the clinical trial setting.

The Exit DBPCFC will initially assess desensitization to 300 mg of peanut; to assess further desensitization, subjects will be administered 600 mg peanut protein, and in those shown to tolerate this exposure (1043 mg cumulative), an additional dose will be made with 1000 mg (2043 mg cumulative). This is equivalent to approximately 8 to 10 peanuts over the course of the day.

The ability to tolerate 1000 mg (2043 mg cumulative) will be assessed as the primary endpoint, and the ability to tolerate 600 mg (1043 mg cumulative) and 300 mg (443 mg cumulative) will be assessed as key secondary endpoints. As discussed in [Section 1.1](#), all of these challenge dose levels are believed to represent amounts of peanut protein in excess of what might typically be encountered in an accidental ingestion of peanut.

1.6 Known and Potential Risks and Benefits to Human Participants

Peanut is a commonly-consumed food and as such has a well-understood safety profile. Except for allergic reactions in subjects with peanut allergy, it does not cause discernible side effects in humans.

In subjects with peanut allergy, many OIT studies have been performed using procedures and dosing similar to those proposed in this study. In general, the safety profile has been very good across the studies, and based on those studies, approximately 80%, 15%, and <1% of the subjects are expected to have mild, moderate, or severe symptoms, respectively, during some point in their dosing with peanut OIT. It is important to note that essentially all AEs have been allergy related, predictable, and reversible. The major atypical AE from peanut OIT that has been reported in the literature is eosinophilic esophagitis (EoE), affecting an estimated 3 to 4% of OIT recipients ([Lucendo et al, 2014](#)), which is thought to be reversible upon dosing cessation.

The up-dosing and daily maintenance doses of peanut OIT may cause allergic symptoms including sneezing, rhinorrhea, urticaria, angioedema, flushing, flares of eczema, ocular, nasal, oral and/or throat pruritus, nausea, vomiting, abdominal discomfort, cough, wheezing, and/or shortness of breath in addition to severe anaphylaxis. The likelihood of a subject experiencing a severe allergic symptom is expected to be lessened by initiating dosing at extremely small amounts of AR101 and by up-dosing under observation in a clinical setting until the maintenance dose is achieved.

There may be a risk that during participation in the trial subjects may decrease their vigilance against accidental peanut ingestion because they believe they are protected from it. This phenomenon has been reported in previous trials; subjects in this trial and their participating families will be warned that they should continue to practice their usual vigilance against accidental ingestion of peanuts or peanut-containing foods.

There is no guarantee that participation in this study will help the subject. The subject may receive placebo during the double-blind treatment period of the study. Information from this study may help researchers to better understand peanut allergy or to develop future tests or treatments to help subjects with this condition.

Please refer to the current edition of the AR101 Investigator's Brochure for further information regarding the safety profile, risks, and benefits of AR101.

2. OBJECTIVES

2.1 Primary Objective

The primary objective is to demonstrate the efficacy of AR101, a pharmaceutical-grade peanut allergen formulation, through reduction in clinical reactivity to limited amounts of peanut allergen in peanut-allergic children and adolescents (ages 4 to 17 years, inclusive).

2.2 Secondary Objectives

[figure not shown]
The secondary objectives are:

- To demonstrate the safety of AR101 as measured by the frequency of AEs, including SAEs.
- To evaluate the immunological effects of peanut OIT therapy.

3. STUDY DESIGN

ARC010 is a European, multicentre, randomized, double-blind, placebo-controlled study. The study design is illustrated in [Figure 1](#).

Figure 1 Study Design

3.1 Screening Period

Subjects 4 to 17 years of age must have a clinical history of allergy to peanut or peanut-containing foods, a serum IgE to peanut of ≥ 0.35 kU_A/L, and/or a SPT to peanut of ≥ 3 mm versus negative control at the time of Screening. Eligible subjects will undergo an initial DBPCFC at the end of the Screening Period (refer to [Section 6.6.1](#)). This DBPCFC

will include both a peanut challenge (defatted peanut flour) and a placebo challenge (artificially peanut-flavored oat flour) on separate days. The Screening DBPCFC will be an abbreviated version of the DBPCFC described in the PRACTALL guidelines, with top challenge doses of 300 mg (444 mg cumulative) of peanut protein or placebo.

For each subject, a Blinded Evaluating Physician (Blinded Assessor) is to be designated to assess the tolerability of the challenge doses presented in the DBPCFC. The Blinded Evaluating Physician, who is assessing and managing subject symptoms on the food challenge days, is not to be involved directly in the oversight of study product dosing or the assessment or management of AEs during the initial escalation, up-dosing, or maintenance phases of the study; nor should he or she be involved in the food challenge material preparation on the food challenge days. To the extent practicable, the same Blinded Evaluating Physician who determines DLS in the Screening DBPCFC should determine DLS in the Exit DBPCFC.

Those subjects who have DLS at or before the 300 mg (444 mg cumulative) challenge dose of peanut protein (measured as 600 mg of peanut flour) will be enrolled into the study. According to a logistical regression analysis performed by the VITAL 2.0 study group using food challenge data from multiple sources, this would select for the more sensitive portion of the peanut-allergic population ([Remington, 2013](#); [Allen et al, 2014](#)). Those who successfully consume and tolerate a 300 mg (444 mg cumulative) dose of peanut protein during the Screening DBPCFC (ie, without manifesting DLS), will be considered screen failures and will not be randomized.

Any subject who is assessed to have had DLS to the placebo part, or both parts, of the Screening DBPCFC (ie, to oat flour as well as peanut flour) will be considered a screen failure and will not be randomized.

Approximately 160 subjects who pass Screening will be randomized 3:1 to either AR101 (active treatment) or placebo using a proprietary interactive response system.

3.2 Treatment Phase

The Treatment Phase comprises 3 periods:

- **Initial Escalation** (2 consecutive days) – Eligible subjects will be randomized and initiate OIT starting at a dose of 0.5 mg of IP, and then increase the dose incrementally at 20 to 30 minute intervals over the course of a single day to a maximum dose of 6 mg. Subjects who fail to tolerate at least a 3 mg dose will be considered escalation failures and will be discontinued from the study. Subjects who tolerate both the 3 mg and 6 mg doses of IP, or who tolerate the 3 mg but not the 6 mg dose, will undergo confirmatory testing of the tolerability of a 3 mg dose the following consecutive day (refer to Initial Escalation Schedule at end of synopsis). Subjects who tolerate this confirmatory dose will enter the Up-dosing Period. Subjects who do not tolerate this confirmatory dose will be discontinued. Therapy details are found in [Section 3](#) and [Section 6](#) of the protocol.

- **Up-dosing Period** – After the initial escalation period, subjects will report to the CRC every 2 weeks to escalate their OIT dose to an expected daily dose of 300 mg of peanut protein. This constitutes the Up-dosing Period. Subjects will receive daily oral dosing of peanut or placebo OIT for approximately 20 weeks, if up-dosing proceeds without holding at, or reducing, a dose level; up to 40 weeks, maximum. All escalation doses will be administered in a CRC or other monitored setting (unless required by a specific institution, no distinction will be drawn between an investigational site, study center office, clinic, or CRC, provided the capability requirements for monitoring and emergency intervention are met by the facility). All up-dosing activities will be performed under direct observation. Therapy details are found in [Section 3](#) and [Section 6](#) of the protocol.
- **Maintenance Period** – Those subjects who reach the target maintenance dose of 300 mg/d of IP will enter an approximately 12-week Maintenance Period of continued dosing at 300 mg/d, which may be extended by up to an additional 4 weeks (for a maximum Maintenance Period duration of 16 weeks), or to a total Treatment Phase duration of 56 weeks, whichever occurs first.

Treatment will be conducted in a double-blind fashion. The IP (AR101 or placebo) will be coded according to subject randomization number. The subjects and the investigational site personnel will be blinded to treatment assignment.

The dose-escalation schedule is described in detail in [Table 1](#) and [Table 2](#).

Table 1 Initial Dose Escalation Schedule

Initial Dose Escalation Schedule		
Day 1 Dose Number	Investigational Product Dose, mg ^a	Cumulative Dose, mg
1	0.5	0.5
2	1	1.5
3	1.5	3
4	3	6
5	6	12

^a All mg doses shown refer to milligrams of peanut protein or the equivalent placebo dose. Doses will be delivered at 20 to 30 minute intervals under direct observation. Capsules are to be opened, contents sprinkled over an age-appropriate food, and mixed thoroughly and consumed. Day 1: Subjects who are unable to tolerate a dose of 3 mg at the end of Day 1 will be considered escalation failures. Subjects who tolerate ≥ 3 mg on Day 1 will return on Day 2 to receive a 3 mg single dose. Day 2: Subjects with either no symptoms or mild symptoms on Day 2 at 3 mg will start daily home dosing at 3 mg on Day 3. Subjects with moderate or severe symptoms at 3 mg on either Day 1 or Day 2 will be considered escalation failures.

Subjects who reach and tolerate 300 mg/d will continue at that dose level for the duration of the Maintenance Period. The first Maintenance Visit occurs 2 weeks after the 300 mg Up-dosing Visit, with visits every 4 weeks thereafter. Any subject unable to achieve a dose of 300 mg/d of peanut protein by 40 weeks will not undergo the Exit DBPCFC.

Table 2 Up-dosing Schedule

Up-dosing Schedule			
Dose Number	Investigational Product Dose, mg (peanut protein or placebo)	Interval (weeks)	Percent Increase from Previous Dose
1	3	2 ^a	n/a
2	6	2	100
3	12	2	100
4	20	2	67
5	40	2	100
6	80	2	100
7	120	2	50
8	160	2	33
9	200	2	25
10	240	2	20
11	300	Enter Maintenance Period	25

^a Interval includes Day 2 of Initial Escalation.

During the treatment period, the subjects will be monitored for the tolerability of IP, as described in [Section 6.7.2](#) and [Section 6.7.3](#).

If a subject discontinues therapy prematurely for any reason, the subject will be followed for safety and asked to return to the CRC 14 to 16 days following his or her last dose of IP to undergo an Early Discontinuation Visit ([Section 6.4](#)). In the event of ongoing AEs, subjects who have discontinued therapy should continue to be followed beyond the Early Discontinuation Visit until such time as the AE has resolved or is assessed to have reached a chronic stable state (a determination that may not be made sooner than 30 days after the Early Discontinuation Visit). Subjects who have GI AEs with prolonged disruption of dosing or who discontinue treatment due to GI AEs will have safety follow-up for 6 months or until chronic or recurrent GI symptoms resolve or stabilize, whichever is last ([Section 7.3.3.2](#)).

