All subjects who tolerate a dose of at least 3 mg on Day 1 will return on Day 2 to receive a single confirmatory 3 mg dose under direct observation.

Subjects with either no symptoms or mild, non-DLS after receiving 3 mg on Day 2 are to start 2 weeks of daily dosing at 3 mg.

Subjects who experience moderate or severe symptoms after receiving the 3 mg dose on Day 2 will be considered escalation failures.

Future dose escalations will occur every 2 weeks with the initial dose increase administered in the CRC.

Protocol ARC010 Synopsis

Up-dosing Period Dosing Schedule

Up-dosing Dose #	Study Product Dose (mg peanut protein or placebo)	Interval (weeks)	% Increase
1	3	2	
2	6	2	100%
3	12	2	100%
4	20	2	67%
5	40	2	100%
6	80	2	100%
7	120	2	50%
8	160	2	33%
9	200	2	25%
10	240	2	20%
11	300	Enter Maintenance Period	25%

Capsules and sachets (introduced during the Maintenance Period) will be opened, contents sprinkled over an age-appropriate food, and mixed thoroughly. The 300 mg capsules will be used for at least the first 2 weeks of dosing during the 12-Week Maintenance Period.

TABLE OF CONTENTS

1.	BACKGROUND AND RATIONALE	20
1.1	Background.....	20
1.2	Clinical Trials of AR101.....	22
1.2.1	ARC001 Trial	22
1.2.2	ARC003 Study.....	25
1.2.3	ARC004 Study.....	25
1.2.4	Open-label Follow-on Study, ARC008	25
1.3	Rationale for Selection of Study Population.....	26
1.4	Rationale for Selection of Investigational Product Regimen (Dose and Duration)	26
1.5	Rationale for the Doses Selected for the DBPCFC	27
1.6	Known and Potential Risks and Benefits to Human Participants	28
2.	OBJECTIVES	29
2.1	Primary Objective	29
2.2	Secondary Objectives	29
3.	STUDY DESIGN	29
3.1	Screening Period.....	29
3.2	Treatment Phase.....	30
3.3	Exit DBPCFC	32
3.4	Open-label Follow-on Study – ARC008	33
3.5	Definition of End of the Study.....	34
3.6	Study Design Safety Considerations.....	34
3.7	Primary Efficacy Endpoint	34
3.8	Secondary Endpoints	34
3.8.1	Secondary Efficacy Endpoints	34
3.8.1.1	Key Secondary Efficacy Endpoints	34
3.8.1.2	Other Secondary Efficacy Endpoints	34
3.8.2	Exploratory Endpoints	35
3.8.3	Safety Endpoints	35
4.	SELECTION AND WITHDRAWAL OF SUBJECTS	35
4.1	Inclusion Criteria	35
4.2	Exclusion Criteria	36
4.3	Premature Subject Termination from the Study	38
4.3.1	Criteria	38
4.3.2	Follow-up of Subjects Who Discontinue Treatment	39
5.	STUDY TREATMENT	39
5.1	Formulation, Packaging, and Labeling	39

5.2	Preparation, Administration, and Dosage	40

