- For **severe symptoms**, the subject should be observed for a minimum of 3 hours after resolution of the symptoms, either at the CRC or an emergency facility, as appropriate. Subject is to be discontinued as an escalation failure
- Any subject deemed to have severe symptoms that include hypoxia, hypotension, or change in mental status (stage 3 anaphylaxis defined in [Appendix 3](#)), or who receives intensive therapy (to be determined by the investigator, but may include such interventions as IV epinephrine, intubation, or admission to an intensive care unit) for an allergic reaction at any time should be discussed with the medical monitor and discontinued from the study.
- If DLSs occur on Day 2, there will be no further dosing. The subject will be asked to return to the CRC 14 to 16 days following the last dose of IP to undergo an Early Discontinuation Visit ([Section 6.4](#)). The subject will continue to be monitored for safety until the Early Discontinuation Visit is completed or any ongoing AEs are resolved, whichever comes first.
- Those subjects who tolerate the single 3 mg dose of IP on Day 2 will be dispensed a 2-week supply of IP at the 3 mg/d dose level. They will be instructed to continue daily oral dosing at home, starting the following day (Day 3), and to continue daily home dosing at that dose level for 2 weeks until next escalation.
- Subjects and parents/guardians will be educated on home dosing instructions per [Section 5.2](#).

On Day 3, the site is to make telephone contact with the subject/subject's parent or guardian to enquire if any AEs (including allergic symptoms) occurred subsequent to the subject leaving the clinic, and to provide assistance in recording of, and responding to, any such events.

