In general, if a subject requires only 1 or 2 doses of antihistamine to treat mild symptoms occurring during the course of the initial escalation, then the initial escalation may continue. If, however, the subject requires a second medication (eg, epinephrine or a beta-agonist) to treat the symptoms, or more than 2 doses of an antihistamine, the initial escalation is to be terminated and the subject is to receive no further OIT, even if the symptoms were assessed to be mild. Use of epinephrine to treat dose-related symptoms, even in the unlikely event that the symptoms are graded as mild, will be cause to terminate the initial escalation.

Moderate symptoms: For moderate symptoms, if the symptoms are not worsening or amassing at a rapid pace, then a stepwise approach to treatment may be taken at the discretion of the investigator. If the first action undertaken is to implement an observation period, the observation period should not exceed 30 minutes before either the symptoms are noted to be resolving or therapy is instituted. Whether treatment is initiated immediately or after an observation period, the subject may be treated first with antihistamines or immediately with epinephrine, as deemed appropriate by the investigator. Other therapies may be added either sequentially or simultaneously, per investigator judgment.

If moderate symptoms occur at any of the doses below 6 mg (ie, up to and including 3 mg), then the desensitization procedure will be discontinued. The decision to discontinue escalation is to be based solely on the determination of whether the allergic reaction was of moderate severity. Although it is generally the case that some form of treatment will be instituted for moderate symptoms, treatment is not a requirement for assessing an allergic reaction as being of moderate severity.

Severe symptoms: For severe symptoms, the actions taken should be to discontinue the initial escalation and administer the appropriate rescue medications. The desensitization procedure will be discontinued regardless of the dose at which the severe symptom or symptoms occurred.

The medical monitor will answer any questions and assist in any decisions related to the study protocol.

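### The Day 2 sentence in the Table 1 note drops the non-dose-limiting qualifier, so as written it sends a child with a mild dose-limiting reaction at 3 mg to home dosing

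*Protocol*

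**What the plan says.** Day 2 of the Initial Escalation is a single supervised 3 mg dose that decides whether a child moves on to daily dosing at home. The protocol states the rule in several places.

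- **Section 3.2, Table 1 note:** "Subjects with either no symptoms or mild symptoms on Day 2 at 3 mg will start daily home dosing at 3 mg". The next sentence reads: "Subjects with moderate or severe symptoms at 3 mg on either Day 1 or Day 2 will be considered escalation failures".
- **Section 3.2, Initial Escalation bullet**, repeated in the synopsis treatment description: "Subjects who do not tolerate this confirmatory dose will be discontinued". The same bullet points to the synopsis schedule: "refer to Initial Escalation Schedule at end of synopsis".
- **Synopsis, Initial Escalation dosing schedule:** "Subjects with either no symptoms or mild, non-DLS after receiving 3 mg on Day 2 are to start 2 weeks of daily dosing".
- **Section 6.3.2.2 (Day 2):** "If DLSs occur on Day 2, there will be no further dosing", and "Those subjects who tolerate the single 3 mg dose of IP on Day 2 will be dispensed a 2-week supply of IP".
- **Section 6.7.4**, on mild symptoms that need a second medication or more than 2 antihistamine doses during initial escalation: "the subject is to receive no further OIT, even if the symptoms were assessed to be mild".

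**The concern.** The note sorts Day 2 outcomes by severity alone: none or mild goes home on 3 mg, moderate or severe is a failure. The rest of the protocol sorts them by whether the dose was tolerated or was dose-limiting. The two schemes agree unless a reaction is mild and also dose-limiting. For that child the note and the stop rules give opposite instructions.

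At stake is the clarity of a go/no-go rule for moving peanut-allergic children aged 4 to 17 from supervised to home dosing. Table 1 is one of the two tables in which Section 3.2 says the escalation schedule is set out in detail, and the protocol states no order of precedence between the table note and the visit procedures.

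**Working it through.** No arithmetic applies. The check is whether a mild dose-limiting reaction can occur under the protocol's definitions and, if so, what each rule does with it.

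**Step 1: Can a mild reaction be dose-limiting?** Yes. Section 6.7.2 lists conditions that a mild reaction should meet to count as tolerated, including confinement to one organ system, no epinephrine, no progression and no objective wheezing. If they are not all met, the dose should be assessed as not tolerated even though symptoms are mild; an investigator who decides otherwise must explain it in the CRF. Section 6.6 likewise says, for food challenges, that mild symptoms may or may not be dose-limiting.

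**Step 2: An example.** On Day 2 a child has a few localized hives and vomits once. Section 6.7.1 grades each symptom as mild. Skin and gut are two organ systems, so under Section 6.7.2 the dose is by default not tolerated.

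**Step 3: Apply each rule to this child.**

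| Place | Test used | Result |
|---|---|---|
| Table 1 note, Day 2 | severity only | home dosing starts |
| Section 3.2 text and synopsis description | tolerated or not | discontinued |
| Synopsis dosing schedule | mild and non-dose-limiting | does not qualify for daily dosing |
| Section 6.3.2.2 | dose-limiting or not | no further dosing |
| Section 6.3.2.2 | tolerated or not | no home supply dispensed |

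The note alone gives the opposite result. Section 6.7.4 would also stop a child whose mild symptoms met its medication criteria, but it is weaker support: it mostly addresses whether a sequence of doses may go on, and its figure is captioned for Day 1.

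**Step 4: Is the omission deliberate?** It does not look so. The note's own Day 1 sentence uses tolerability of 3 mg as its test, and the parallel synopsis sentence carries the qualifier. A dropped qualifier is the simplest explanation.

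**Step 5: Does it reach the analysis?** Under Section 9.2.1 anyone who stops OIT before the Exit DBPCFC is a treatment failure, whether or not labelled an escalation failure. The label does not change the timing of unblinding either: Sections 4.3.1 and 6.12 leave both groups blinded until database lock. Both have the same Early Discontinuation Visit, 14 to 16 days after the last dose.

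**The case against.** The strongest reply is that the note is shorthand and the surrounding text supplies what is missing. Section 3.2 closes by referring to Sections 6.7.2 and 6.7.3 for tolerability, and Section 6.7.2 is where mild reactions are divided into tolerated and not tolerated. The tolerance rule stands in the same section, just above the table. Section 6.3.2.2 has its own unqualified line letting subjects with mild symptoms continue, and it is read without difficulty because the dose-limiting bullet follows in the same list. Nor does the note say that only moderate or severe symptoms are failures.

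Most of this stands, and it limits the point to low severity. It does not remove it. The note has no qualifier or cross-reference of its own, and a reader using the table alone gets the wrong instruction.

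Three stronger readings are tempting and are not supported:

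- **That children will be sent home on a dose they failed.** Section 6.3.2.2 controls dispensing and excludes them.
- **That failure counts or the primary result are distorted.** Stopped subjects are failures under Section 9.2.1 whatever they are called.
- **That the labelling of escalation failures is a fault of Table 1.** The synopsis schedule also names only moderate or severe Day 2 symptoms as failures, and Section 6.3.2.2 stops dosing for dose-limiting symptoms without using that label.

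**Conclusion.** The point holds as a low-severity inconsistency in safety text. One sentence in the Table 1 note lacks a qualifier that its synopsis counterpart has and, taken literally, contradicts Sections 3.2 and 6.3.2.2 for a child with a mild dose-limiting reaction on Day 2. No design decision is in question, and power, alpha and the primary analysis are untouched.

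The number of children concerned cannot be estimated, since the protocol gives no rate of such reactions. It is probably small: Section 6.7.2 expects most mild reactions to dosing to meet the tolerability criteria. The conclusion assumes that *dose-limiting* and *not tolerated* mean the same for the Day 2 dose, which is how the two bullets of Section 6.3.2.2 use them, and that sites follow Section 6.3.2.2 when dispensing.

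**What to change.** In the Table 1 note, change the Day 2 condition to *no symptoms or mild, non-dose-limiting symptoms*, matching the synopsis schedule. Then add: *Subjects with dose-limiting symptoms of any severity on Day 2 receive no further dosing (Section 6.3.2.2).*

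Refer to Section 6.3.2.2 rather than 6.7.2. Section 6.7.2 gives treatment with 2 antihistamine doses as an example of a dose not tolerated, while Section 6.7.4 lets initial escalation continue after 1 or 2; that separate difference should not be brought into the note.

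Do not label these subjects escalation failures in Table 1 alone. Its failure sentence now agrees with the synopsis schedule, and a one-sided change would create a new mismatch. If the label is wanted, add it to the synopsis schedule, the Table 1 note and Section 6.3.2.2 together; otherwise leave it out.

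The cost is a wording change in one table note, with no added visits, procedures or subjects.
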